### 5.1.11 Other Therapy:

All standard of care therapy provided for multiple myeloma subjects undergoing autologous transplant will be allowed.

### 5.1.12 At day +15 (+/-3) and day +60 (+/-3) post-transplant

All subjects will receive tetanus vaccines as intramuscular injection. Platelets will be transfused if platelet count is < 30k on day +15 to allow for the intramuscular injection.

### 5.1.13 Immune evaluation assays (anti-tetanus & immunophenotyping)

Assays will be performed on day +15 (+/- 3 days), +30 (+14days), day+70 (+14days), day+100 (+/-10 days), and Day 180(+/-10) post-transplant on both groups.

## **5.2 Post transplant Myeloma Management:**

5.2.1 All post-transplant myeloma staging and therapy will be based on local standard of clinical practice for myeloma subjects. Subjects will undergo *Euroflow-based* MRD staging if they are deemed to be close to CR (serum protein electrophoresis < 0.1 gdL, but serum immunofixation positive) based on IMWG criteria.

5.2.2 For all subjects, post-transplant myeloma specific therapy may not be started before the day 100 (+/-10) visit on this protocol. The only exception would be disease progression that occurs before day+100, in which case the subject will be taken off study.

5.2.3 Subjects on this protocol may not enroll on other treatment/interventional protocols for the first 100 (+/-10) days post-transplant. The only exception would be disease progression before day+100, in which case, the subject is off study.

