## **Section 1.0 Objectives:**

### **Hypotheses**

1. The abundance of immune suppressive cells in G-PBSC grafts results in poor immune reconstitution post AHSCT, leading to higher risk for infection and myeloma relapse.
2. Depletion of immune suppressor cells from G-PBSC graft will allow a robust *in vivo* expansion of the adoptively transferred lymphocytes as well as a robust recovery of antigen specific tetanus immune response post-transplant compared with the control group.
3. It is safe and feasible to deplete all immune suppressive cells from G-PBSC grafts by positively selecting CD34+ cells from G-PBSC grafts and combining that with an autologous donor lymphocyte infusion product.

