### **1.2 Secondary:**

- 1- To compare post-transplant recovery of innate and adaptive immune cells (CD8, CD4, CD19, NK,  $\gamma\delta$  T-cells), in addition to T-cell phenotype markers between the two arms.
- 2- To compare post-transplant recovery of T-reg and MDSCs between the two arms.
- 3- To compare progression free survival (PFS) at 2 years post-transplant

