### **5.6 Removal from the study**

Subjects who for whatever reason do not meet the cardiac ejection fraction, pulmonary function test requirement or develop significant organ dysfunction before the transplant admission will be removed from the study.

The investigator will withdraw a subject from the study treatment whenever:

1. Continued participation is no longer in the subject's best interests. Reasons for discontinuing treatment may include the occurrence of a SAE or an inter-current illness. These subjects will be taken off treatment and followed according to the study calendar.
2. The subject requests to end treatment.
3. Subjects who fail to collect a minimum of 6 million CD 34 cells/kg body weight at the end of 1st day of Leukapheresis will be either removed or transferred to arm 2 of the protocol after discussion with the PI.

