## Section 7.0 Study Parameters

Examinations and Assessments	Baseline (Screening)	Pre-Transplant (SCT)				Transplant	Post Transplant Period										Follow up Period
	Pre vaccine	Vaccine (day -19)	Day -12 to -9	Day -11 to -7	Day -6 to -4	AHSCT Hospitalization	Day + 7	Day +15	Day +30	Day +60	Day +70	Day +100 (mo. 3)	Day +130 (mo. 4)	Day +150 (mo. 5)	Day +180 (mo. 6)	Day +365 (1 yr)	Survival status (2 years)
Window Days for Study Visit 	-30 days (+/-10 days)					Day 0		+/-3	+14	+/-3	+14	+/-10	+/-7	+/-7	+/-10	+/-30	+/-30 days
Informed Consent	X																
Inclusion/Exclusion Criteria	X																
Pregnancy testing	X 																
Medical History	X																
Clinical Assessment	X 																
Data collection to assess organ function (labs) 	X																
Disease response 	X												X			X	X
Data collection for Disease Assessment													X				

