## **Section 10.0 Statistical Considerations:**

### **10.1 Primary Objectives**

Given the known lack of vaccine response in the first few months post autologous stem cell transplantation, we intend to look for evidence of vaccine response in the experimental arm via increase in tetanus specific T-cell Elispots and anti-tetanus antibody (Elisa) on days 30, 70, 100 and 180 post-transplant. Given the pilot/explorative nature of this trial and the lack of good pre trial assumptions about vaccine response, we will evaluate the vaccine response by Elisa and Elispot on days 30, 70, 100 and 180 will be compared between groups using a Mann-Whitney test.

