### **10.2 Secondary Objectives**

For the secondary objectives, engraftment, development of any auto immune side effects, and infections will be treated as binary variables. Chi-square tests will be used to compare each of these 3 outcome variables between the two groups, respectively. A Wilcoxon signed-ranks test will be employed to test the change in absolute lymphocyte (ALC), absolute monocyte counts (AMC), immune cells (T cells CD8, CD4), natural killer cells,  $\gamma\delta$  T-cells, T-reg and MDSCs) at days 15 and 30 post AHSCT from the baseline among each group, respectively. Wilcoxon signed-ranks test will be further used to compare the change of change in ALC, AMC and immune cells between the two groups at days 15 and 30 post- AHSCT, respectively.

Generalized linear mixed models will be employed to compare the change pattern of ALC, AMC and immune cells between the two groups over the entire follow up periods. Time to relapse and overall survival will plotted using the methods of Kaplan and Meier and the log rank test will be used to compare the time to event curves between the two treatment groups.

Lastly, as an explorative objective will also be depth of anti-myeloma response as evaluated by the standard IMWG criteria, including the rate of sCR, and subsequent MRD status for the subjects in sCR.

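### Sections 5.2.2 and 5.2.3 take subjects who progress before day +100 off study, and nothing keeps them in survival follow-up or the later vaccine readouts

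*Combined protocol and SAP*

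**What the plan says.** Section 5.2 restricts two things until about day 100: starting myeloma therapy (5.2.2) and joining other interventional protocols (5.2.3). Each restriction ends with the same consequence for early progression. In 5.2.2 it reads "The only exception would be disease progression that occurs before day+100, in which case the subject will be taken off study". In 5.2.3 it reads "The only exception would be disease progression before day+100, in which case, the subject is off study". Neither section says which procedures stop.

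Section 5.6, item 1, words things differently for subjects withdrawn from treatment in their own best interest: "These subjects will be taken off treatment and followed according to the study calendar". Progression is not among the reasons named there.

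The analyses that depend on later data are:

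- the primary vaccine comparison, in which ELISA and ELISPOT results "on days 30, 70, 100 and 180 will be compared between groups using a Mann-Whitney test" (Section 10.1);
- the secondary objective "To compare progression free survival (PFS) at 2 years post-transplant" (Section 1.2);
- the time-to-event analysis: "Time to relapse and overall survival will plotted using the methods of Kaplan and Meier", with a log-rank comparison (Section 10.2).

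The Study Parameters table in Section 7.0 has a survival-status column at 2 years (+/-30 days). Section 10 gives no analysis population, censoring rule or missing-data method. Section 5.5 allows for screen failures but not for loss after randomisation.

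**The concern.** A randomised subject leaves the study because of an outcome. Two analyses are exposed.

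**Overall survival.** If contact stops at progression, the subject is censored when the risk of death has just risen. Kaplan-Meier and log-rank assume that censored subjects have the same later risk as those still followed, and here they would not.

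**Vaccine response.** The first hypothesis in Section 1.0 is that suppressive cells in the graft impair immune recovery, "leading to higher risk for infection and myeloma relapse". If that is right, early progressors tend to be poor responders, and removing them selects on something related to the primary endpoint. A subject who progresses just after day 100 stays in, so the boundary is also arbitrary for the day 180 readout.

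**Working it through.** **1. What the text supports.** Sections 5.2.2 and 5.2.3 say off study; Section 5.6 item 1 says off treatment but followed. The protocol therefore has wording for keeping a subject in follow-up and does not use it for early progressors. No other section restores their follow-up. Stopping is the natural reading, but it is an inference from an undefined term.

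**2. The plan's own figure.** Section 10.5 states at least 80% power for a two-sided 5% Mann-Whitney test, 10 per arm, d = 1.36, Normal data. Scale n by the asymptotic relative efficiency 3/pi and use the noncentral t:

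- effective n per arm = 10 x 3/pi = 9.55
- noncentrality = 1.36 x sqrt(9.55/2) = 2.97
- power = 79.997%, so the stated figure reproduces. (A simulation of the exact test gives 77.9%.)

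By the same method, losing values at one readout gives:

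| Values available | Power at d = 1.36 | d detectable with 80% power |
|---|---|---|
| 10 vs 10 | 80.0% | 1.36 |
| 10 vs 9 | 77.6% | 1.40 |
| 9 vs 9 | 75.1% | 1.44 |
| 10 vs 8 | 74.6% | 1.45 |

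**3. How many subjects.** The documents give no rate of progression before day 100, so p is assumed at 2-10%. Expected removals = 20p. Chance of at least one = 1 - (1 - p)^20.

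**4. Overall survival.** Let q be the share progressing early, S_n the 2-year survival of the others and S_p that of early progressors. True survival is q x S_p + (1 - q) x S_n. With early progressors censored at removal, Kaplan-Meier estimates about S_n. The overstatement is q x (S_n - S_p). Assume S_n = 90% and S_p = 30-70%, and take q = p.

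| p | Expected removals of 20 | Chance of at least one | Overstatement of 2-year survival |
|---|---|---|---|
| 2% | 0.4 | 33% | 0.02 x (0.20 to 0.60) = 0.4 to 1.2 points |
| 5% | 1 | 64% | 0.05 x (0.20 to 0.60) = 1 to 3 points |
| 10% | 2 | 88% | 0.10 x (0.20 to 0.60) = 2 to 6 points |

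If two removals fall in one arm of 10, q = 20% there, and that arm is overstated by 0.20 x (0.20 to 0.60) = 4 to 12 points.

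**5. Progression-free survival and time to relapse.** The progression that triggers removal is the event, so nothing is lost if it is recorded and counted. If it were censored instead, and 2-year progression-free survival in the others is assumed to be 75%, the true value is (1 - q) x 75%: 73.5% at q = 2% and 67.5% at q = 10%. Reading 75% would then overstate it by 1.5 to 7.5 points.

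**6. Vaccine response.** Suppose early progressors respond s SD lower in both arms. Removal raises an arm's mean by p x s, so the difference (experimental minus control) shifts by s x (p_E - p_C). With p_E = p_C the shift is zero. With p_E = 0, p_C = 20% (two removals, both control) and s = 0.5 to 1.5, it is -0.10 to -0.30 SD. With the rates reversed the sign reverses. For scale, the design's detectable effect is 1.36 SD.

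**The case against.** **Off study may not mean lost to follow-up.** No sentence forbids survival contact, and the 2-year survival column has no exclusion for progressors. This stands as far as it goes: a reader might infer that the protocol expressly ends survival follow-up, and it does not. But two sections give the same instruction, and a site following them would have no basis for continuing.

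**The 2-year endpoint is safe.** A reader might infer that 2-year progression-free survival is biased. The documents do not support that, because the triggering progression is itself the event. The informative censoring concerns overall survival, which appears only as an analysis line in Section 10.2 and is not a listed objective. For the same reason, the loss should not be expressed as a share of progression-or-death events: the removed subjects can be counted there, and the documents give no expected number of deaths.

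**Little is lost before day 100.** The schedule plans no blood or urine disease assessment between baseline and day 100, and eligibility requires at least a partial response to induction. Much early progression would surface around the day 100 visit, when the sample is also due. Days 30 and 70 are mostly unaffected. The text of Section 9 ends adverse event collection at day 100 for everyone (the table ticks later visits), so on that text the safety loss is only the interval from progression to day 100. All of this stands.

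**The direction of vaccine bias is unknown.** A reader might infer that the rule hides a benefit of the experimental graft. That needs unequal early-progression rates, which the documents do not give, and poorer responses in progressors. Section 2.6 concedes there is no clear direct evidence linking post-transplant immune suppression to relapse.

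**Samples after new therapy are contaminated.** The steroid restriction to day +181 shows that the sponsor cares about this, and stopping immune sampling is arguable in a 20-subject pilot. But Section 5.2.2 lets any subject start myeloma therapy from the day 100 visit, so retained subjects' day 180 samples may also be on therapy. Contamination is a reason to flag samples; it is no reason to lose survival status.

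**Conclusion.** The point holds in limited form. As written, early progressors leave the study with no stated follow-up, so overall survival would be informatively censored and the later vaccine readouts would lose subjects on an outcome-dependent basis. Progression-free survival and time to relapse are sound only if the progression is counted, which should be written down.

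The size rests on assumptions: 0.4 to 2 of 20 subjects at early-progression rates of 2-10%, and an overall-survival overstatement of 0.4 to 6 points under the survival figures assumed above. No size or direction can be given for vaccine bias. The case for amending is strongest for survival follow-up and event counting; continued immune sampling after new therapy is secondary and more debatable.

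**What to change.** In Sections 5.2.2 and 5.2.3, replace *off study* with wording that the subject leaves the protocol's restrictions but stays in follow-up in the randomised arm. Then state:

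- the progression date is recorded and counted as the event for progression-free survival and time to relapse;
- the new therapy and its start date are recorded;
- survival status is collected to 2 years;
- where the subject agrees, the already scheduled day 100 and day 180 samples are still drawn, and those taken after new therapy are flagged;
- the vaccine comparison is reported with and without the flagged samples.

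The cost is two amended sentences, a short addition to Section 10, and a survival contact plus a few flagged samples for an expected 0.4 to 2 subjects at the assumed rates. Treatment at progression is unchanged.

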### **5.3 Possible Complications:**

Subjects in the experimental arm (group 1) will be closely monitored after day zero for any possible treatment related toxicity. These toxicities may include but are not limited to:

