**Schema:**

As shown in the schema above:

- 1- Subjects in all groups will receive tetanus vaccine 7-10 days prior to mobilization.
- 2- Subjects in group 1 will have mononuclear cells collected and frozen 7-10 days after tetanus vaccination pre-transplant. These subjects will then receive a CD34+ selected graft on day 0 and autologous donor lymphocyte infusion (DLI) on day +7.
- 3- Subjects in group 2 will receive a standard G-CSF mobilized graft on day 0 without any DLI post-transplant.
- 4- Subjects in all groups will receive G-CSF as subcutaneous injections daily (10 µg/kg) x 5 days starting on day -11 (following the DLI pheresis in the experimental group). Subjects will receive one dose of plerixafor, a stem cell mobilizer, followed by pheresis on the next day to collect G-PBSC graft, with the goal of  $> 6.0 \times 10^6$  CD34+ cells/kg.
- 5- On day of G-PBSC pheresis, the graft in group 2 will be analyzed for CD34, lymphocyte content, and T-reg and MDSCs (cell differential and flow cytometry). Then it will be processed and frozen as per local institutional standards.
- 6- The stem cell product will start to be washed while waiting for the CD34+ content to be known. CD34+ stem cells will then be selected out of the G-PBSC mobilized graft the same day using clinical grade CD34+ magnetic beads and Clinimacs device from Miltenyi as per manufacturer's instructions and as described below. The CD34 content will be analyzed before freezing in liquid nitrogen.
- 7- The subjects in all groups will receive high dose chemotherapy Melphalan at 200 mg/m^2 on day -1.

8- On day 0, subjects in group 1 will receive the thawed CD34+ stem cell graft, while subjects in the group 2 will receive the standard thawed G-PBSC graft. Transplanted CD34+ stem cell dose both groups will be in the range of 2-10 X 10^6/Kg body weight.

9- On day +7 post-transplant, the stored autologous donor lymphocyte product in group 1 will be thawed and infused back to the subjects.

10- **No planned G-CSF post-transplant** (unless medically deemed necessary due to slow engraftment by day 15)

11- Subjects will be followed closely in the hospital until engraftment and resolution of all transplant related toxicities.

12- Subjects will be closely evaluated for any trial related adverse events, specifically: delayed engraftment, auto-immune side effects (autologous graft versus host disease), and infections.

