#### *2- Autoimmunity (including autologous graft versus host disease autoGVHD):*

Subjects will be closely monitored for any clinical evidence of auto-immunity secondary to excessive immune suppressor cells depletion. Subjects can be treated according to the severity and organ involved based on physician discretion after consulting with the study PI.

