#### *3- Severe lymphopenia:*

Has been described in CD34+ selected AHSCT. In this trial, the chance of lymphopenia is small, since subjects will receive a DLI product on day +7, and these lymphocytes have shown evidence of accelerated *in vivo* expansion in the past. Nevertheless, we will closely watch subjects for lymphopenia beyond the general expected range at 4 weeks post AHSCT. If three consecutive subject's had ALC equal or <1000 cells/ $\mu$ l at 4 weeks post AHSCT, further accrual will be held until their ALC >1000 with no infectious complications (including: CMV, EBV, Adeno- virus, mold). These subjects will be closely monitored for infections (CMV, EBV, adeno virus screening on lymphopenic subjects is optional).

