## **Section 9.0 Toxicity and Adverse Event Reporting Guidelines:**

This protocol will comply with monitoring and adverse event reporting requirements of the UNMC Fred & Pamela Buffett Cancer Center Data Monitoring plan. The protocol will adhere to both institutional IRB and FDA guidelines for toxicity reporting.

All subjects will be closely followed for toxicity from between the start of any protocol intervention and day 100 during the study and all grade 3 or 4 adverse events (or highly unusual grade 2 adverse events) will be recorded on the CRF.

Per NCI guidelines, Serious Adverse Events (SAEs) and Adverse Events (AEs) will be assessed and graded by reports from subjects to their physician/Investigator and by physical examinations. SAEs and AEs will be graded and toxicity assessed using the revised NCI CTCAE version 5.0. AEs will be followed until resolution, return to baseline or  $\leq$  grade 1 levels. The outcome of all SAEs will be graded as resolved; recovering; ongoing; resolved with sequela; fatal.

SAEs will be followed until resolution, return to baseline or  $\leq$  grade 1 levels, death, or until no further improvement is reasonably expected. Deaths occurring within 30 days of study treatment regardless of relationship will be reported to the UNMC DSMC.

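### Section 5.3 adds group 1 monitoring and optional viral screening to surveillance common to both arms, and Section 10.2 does not separate infections found only by screening, so a group 1 excess could partly reflect closer looking.

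*Combined protocol and SAP*

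**What the plan says.** **Text worded for group 1.** Section 5.3 (Possible Complications) opens: "Subjects in the experimental arm (group 1) will be closely monitored after day zero for any possible treatment related toxicity". Three numbered items follow: engraftment failure, autoimmunity and severe lymphopenia. The autoimmunity item reads: "Subjects will be closely monitored for any clinical evidence of auto-immunity secondary to excessive immune suppressor cells depletion". The lymphopenia item describes subjects who receive the day +7 lymphocyte infusion, which only group 1 does. On infection it says: "These subjects will be closely monitored for infections (CMV, EBV, adeno virus screening on lymphopenic subjects is optional").

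**Text common to both arms.** Schema item 12 says: "Subjects will be closely evaluated for any trial related adverse events, specifically: delayed engraftment, auto-immune side effects (autologous graft versus host disease), and infections". Section 9.0 says: "All subjects will be closely followed for toxicity from between the start of any protocol intervention and day 100". It also sets one recording threshold for the CRF: grade 3 or 4 events, or highly unusual grade 2 events. Section 7.3 lists opportunistic infections among the things to record after transplant. The Section 7.0 calendar has a single adverse-event row and a single blood-count row including ALC, with no split by arm, although it labels rows for group 1 where the arms differ.

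**The comparison.** Section 10.2 states that "engraftment, development of any auto immune side effects, and infections will be treated as binary variables", and then: "Chi-square tests will be used to compare each of these 3 outcome variables between the two groups, respectively". It gives no case definition, grade or time window for infection, does not tie the outcome to the Section 9.0 threshold, and is silent on detections made only by screening.

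**The concern.** A yes/no infection outcome depends on how hard each arm is examined. The only viral screening text in the protocol sits in the group 1 complications list. It is optional and carries no schedule. No blinding is described, and the extra pheresis and the day +7 infusion identify group 1 to the treating staff. If lymphopenia is commoner or more closely watched in group 1, testing will be too, and a viral detection without illness could be counted as an infection under Section 10.2.

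Safety is a primary objective (Section 1.1), and Section 2.5 names infection as an excess harm of CD34-selected grafts. With 10 subjects per arm, readers will look at raw counts, so a few additional detections in one arm can shape the safety message.

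**Working it through.** **Plan's own figure.** The documents give no rate, difference or power for the infection comparison. The one power statement (Section 10.5: at least 80% at d = 1.36) concerns the vaccine response. It reproduces at 80.0%, using the noncentral t with the sample size scaled by 3/π, but has no bearing here.

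**Inputs from the documents.** There are 10 subjects per arm (Section 5.5). The test is chi-square at P<.05 without multiplicity correction (Sections 10.2 and 10.5). Section 2.5 cites 45% CMV infection by antibody-titre rise, and a VZV risk of 23-50% in the first year.

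**Assumptions.** The documents give none of the following:
- b, the all-infection risk found without screening, is equal in both arms at 20%, 35% or 50%.
- Screening detects a virus in 45% of screened subjects who would otherwise count as uninfected. This borrows the CMV titre figure; Section 5.3 names no assay.
- s, the fraction of group 1 screened, is 25% or 50%. No one in group 2 is screened.
- Every screening detection is counted as an infection.

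**Formula.** Observed group 1 risk p1 = b + s × 0.45 × (1 − b). Observed group 2 risk p2 = b. For example, b = 0.20 and s = 0.50 give p1 = 0.20 + 0.50 × 0.45 × 0.80 = 0.38, a spurious excess of 18 points.

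All 10 v 10 tables were enumerated exactly with the uncorrected chi-square. The last two columns give the probability of P<.05 with group 1 higher, and of a numerically higher group 1 count.

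| b | s | p1 v p2 | Significant, group 1 higher | Group 1 count higher |
|---|---|---|---|---|
| 20% | 0 | 20% v 20% | 1.5% | 39% |
| 20% | 25% | 29% v 20% | 4.8% | 58% |
| 20% | 50% | 38% v 20% | 11.1% | 75% |
| 35% | 0 | 35% v 35% | 1.9% | 41% |
| 35% | 25% | 42% v 35% | 4.2% | 54% |
| 35% | 50% | 50% v 35% | 8.3% | 67% |
| 50% | 0 | 50% v 50% | 2.1% | 41% |
| 50% | 25% | 56% v 50% | 3.7% | 51% |
| 50% | 50% | 61% v 50% | 6.2% | 61% |

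The uncorrected test needs at least 4 v 0, 6 v 1 or 7 v 2 to reach P<.05, so false significance stays uncommon while the distortion of raw counts is larger. A continuity correction or Fisher's exact test would lower the significance column.

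**Sensitivity.** If 50% of group 1 and 25% of group 2 are screened, the significant excess occurs in about 4-5% of trials over the same base risks.

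**The case against.** The strongest reply is that the control arm is monitored. Section 9.0 follows all subjects to day 100 with one recording threshold, Schema item 12 covers infections and autoimmune effects for subjects generally, Section 7.3 records opportunistic infections, and the calendar treats the arms alike for adverse events and ALC. Screening is optional and tied to lymphopenia, which Section 5.3 expects to be uncommon, and nothing bars the same tests in group 2. The comparison is one of several uncorrected exploratory tests in a 20-subject pilot, and the bias would overstate harm in the experimental arm, the cautious direction.

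Most of this stands, and it limits the point to an extra layer above a common floor. It does not remove the point. Section 5.3 still names one arm, Section 10.2 does not adopt the Section 9.0 threshold, and Section 7.3 lists opportunistic infections alongside adverse events. A screening-only detection is therefore not clearly excluded.

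A reader might also infer something larger from the two CMV figures in Section 2.5. Screening all of group 1 and none of group 2 would give 0.02 + 1 × (0.45 − 0.02) = 0.45 against 0.02: a 43-point excess, significant in about 65% of trials. The documents do not support this. The 2% is CMV pneumonia alone, whereas Section 10.2 compares infections of any kind, and nothing suggests that every group 1 subject and no control would be screened.

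**Conclusion.** The point holds as a possibility of differential detection of infection, of unknown size. Under the stated assumptions, partial screening of group 1 alone raises the chance of a spurious significant excess from about 2% to about 4-11%, and the chance of a higher group 1 count from 39-41% to about 51-75%. These figures rest on assumed base risks, the borrowed 45%, the assumed screening fractions, and every detection being counted. Low-grade detections left unrecorded, or screening used in both arms, would reduce them.

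Three stronger readings are not supported. Group 2 is not left unmonitored. The safety comparison is not uninterpretable: an excess in group 1 simply could not be fully separated from closer looking. Nor is the screening mechanism shown for autoimmune events, because Section 5.3 looks there for clinical evidence rather than a laboratory result, and the working above does not address them. The change is worth making because safety is a primary objective and the remedy is inexpensive.

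**What to change.** 1. Reconcile Section 5.3 with Schema item 12 and Section 9.0, so that it is clear whether the same assessments apply to both arms. Which surveillance to use is for the investigators to decide.
2. In Section 10.2, define the compared infection outcome as clinically apparent (symptomatic) infection within one stated window, with the same definition in both arms. An infection should not count merely because a screening result was treated; otherwise screening re-enters the outcome through treatment.
3. List screening-only detections separately by arm, with the number of subjects tested in each.

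The cost is protocol wording and one outcome definition, and no additional test is required. The downside is that screening-only detections leave the compared outcome. The separate listing keeps them visible. Judging symptoms without blinding still leaves some room for unequal ascertainment.
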